9.5.4 Regulatory Reporting Requirements for SAE

- Prompt notification by the Investigator to safety reporting group of an SAE is essential so that legal obligations and ethical responsibilities towards the safety of participants and the safety of a study treatment under clinical investigation are met.
- Mereo have a legal responsibility to notify both the local regulatory authority and other regulatory agencies about the safety of a study treatment under clinical investigation.
- Investigator safety reports must be prepared for suspected unexpected serious adverse reactions (SUSARs) according to local regulatory requirements and will be forwarded to Investigators as necessary.
- An Investigator who receives an Investigator safety report describing an SAE or other specific safety information (e.g. summary or listing of SAEs) will file it along with the Investigator's Brochure and will notify the IRB/IEC, if appropriate according to local requirements.

9.5.5 Pregnancy

- Details of all pregnancies in female participants and female partners of male participants will be collected after the start of study treatment and until 5 half-lives (4 days) after the last dose.
- If a pregnancy is reported, the Investigator should inform the safety reporting group within 24 hours of learning of the pregnancy and should follow the procedures outlined in [Appendix 5](#).
- Abnormal pregnancy outcomes (e.g. spontaneous abortion, fetal death, stillbirth, congenital anomalies, ectopic pregnancy) are considered SAEs.

Partner Pregnancies

Pregnancy outcomes must be collected for the female partners of the subjects who took study treatment in this study. Pregnancy itself is not regarded as an AE unless there is suspicion that the study treatment may have interfered with the effectiveness of a contraceptive medication. If a pregnancy is reported for a subject's partner, study treatment will be immediately discontinued. The outcome of all pregnancies (spontaneous miscarriage, elective termination, normal birth, or congenital abnormality) must be followed and documented. A follow-up report should be sent with any new information regarding the pregnancy and the outcome of the birth.

9.6 Treatment of Overdose

For this study, any dose of alvelestat greater than 240 mg bid within a 24-hour time period will be considered an overdose.

There is no specific treatment for an overdose. Any treatment should be supportive as indicated by the subject's condition.

In the event of an overdose, the Investigator/treating physician should:

- 1) Contact the study PI immediately.
- 2) Closely monitor the participant for AE/SAE and laboratory abnormalities until alvelestat can no longer be detected systemically (at least 3 days).
- 3) Obtain a plasma sample for PK analysis within 3 days from the date of the last dose of study treatment if requested by the study PI (determined on a case-by-case basis).
- 4) Document the quantity of the excess dose as well as the duration of the overdosing in the CRF.

Decisions regarding dose interruptions or modifications will be made by the Investigator in consultation with the Study PI as necessary based on the clinical evaluation of the participant.

9.7 Pharmacokinetics

Sparse PK sampling will be performed before and after study treatment dosing as detailed in the SoA and Study Manual.

- Blood samples of approximately 3 mL will be collected for measurement of blood concentrations of alvelestat as specified in the SoA. Instructions for the collection and handling of biological samples are in the MOP. The actual date and time (24-hour clock time) of each sample will be recorded.

9.8 Pharmacodynamics

Pharmacodynamic markers form the secondary efficacy endpoints in this study and are covered in Section 9.2.1.

10.0 STATISTICAL CONSIDERATIONS

10.1 Sample Size Determination

Over the course of the study, 15 participants will be randomized in a 2:1 ratio to receive one of the following: alvelestat or placebo on top of SoC or SoC alone .

The primary objective of the study is safety and tolerability. All efficacy analyses are considered exploratory and hypothesis-generating. This is a pilot study and it is not formally powered based on any specific endpoint. Sample size has been set to minimize the number of patients exposed, but still large enough to give adequate safety and tolerability data to support progression of further development, to support estimates on the PK of alvelestat in the target population and to examine for signals on mechanistic and clinical outcome effect.

10.2 Populations for Analyses

For purposes of analysis, the following populations are defined:

Population	Description
Enrolled Set	The Enrolled Set will include all participants who sign the ICF
Full Analysis Set	The Full Analysis Set will include all subjects who signed the ICF and were subsequently randomized into the study. Subjects will be analyzed according to randomized treatment (alvelestat or placebo). The FAS will be used for efficacy analyses.
Safety Set	All randomized participants who take at least 1 dose of study drug. Participants will be analyzed according to randomized treatment. The Safety Set will serve as the primary population for the analysis of safety and tolerability primary endpoint. Subjects will be analyzed according to randomized treatment (alvelestat or placebo)
Per-Protocol Set	Used for sensitivity testing and signal detection for efficacy analyses. The Per-Protocol Set includes all participants from the Full Analysis Set who have been treated according to the protocol and fulfil the following criteria: 
 1) All inclusion/exclusion criteria affecting efficacy satisfied 2) Absence of relevant protocol violations with respect to factors likely to affect the efficacy of alvelestat treatment. 3) Adequate alvelestat compliance Subjects will be analyzed according to randomized treatment.
PK Set	The PK Set will include all participants randomized to the alvelestat arm in the Safety Set who have at least 1 evaluable serum concentration.

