The SAP will be developed and finalized before database lock and will describe the selection of participants to be included in the analyses and procedures for accounting for missing, unused, and spurious data. Below is a summary of planned statistical analyses of the primary and secondary endpoints.

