	
ventilation, high flow oxygen, or ECMO) at Days 5, 10 and 60
 
 • Length of hospital stay • Length of ICU stay 
Time to room air (those on supplemental oxygen at Baseline)

The effect of alvelestat on disease severity
	
By treatment group (alvelestat/placebo):
 
 • Percentage of patients deteriorating (>1 and >2 increase in WHO 9-point ordinal scale*) at Day 5, Day 10, Day, Day 29 and Day 60 
Percentage of patients improving (>1 and >2 decrease in WHO 9-point ordinal scale) at Day 5, Day 10, Day 29 and Day 60

To explore Pharmacokinetics (PK) in patients with COVID-19
	
Plasma PK (sparse sampling taken pre or 1-2 hours post study drug dosing) in participants randomized to alvelestat.

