7.3 Analysis Populations

Summaries and analysis of safety data will be presented for the Safety Analysis Population. Summaries and analysis of efficacy data will be presented for the intent-to-treat (ITT) population.

- Intent to treat (ITT): Will consist of all randomized patients. Efficacy will be evaluated as randomized.
- Modified intention to treat (mITT): Will consist of randomized participants that have baseline and at least one follow-up assessment available.
- Per protocol population (PP): Will consist of all patients in ITT without any major protocol deviations (determined prior to database lock) deemed to have an effect on efficacy analyses.
- Safety set (SS): Will consist of all randomized and treated patients (at least one dose). Safety will be evaluated by actual treatment.

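### The protocol assigns safety data by randomized arm and the SAP by treatment received, and the PK Set follows randomization; one rule should be fixed before database lock

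*Protocol*

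**What the plan says.** Protocol 10.2 defines the Safety Set as "All randomized participants who take at least 1 dose of study drug. Participants will be analyzed according to randomized treatment", and the last sentence of the same definition repeats the as-randomized rule. Between the two it gives the set its role: "The Safety Set will serve as the primary population for the analysis of safety and tolerability primary endpoint".

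SAP 7.3 defines a safety set with the same membership (randomized and at least one dose), but with the other assignment rule: "Safety will be evaluated by actual treatment".

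For pharmacokinetics, protocol 10.2 says: "The PK Set will include all participants randomized to the alvelestat arm in the Safety Set who have at least 1 evaluable serum concentration". The SAP defines no PK set. Its Table 3 (section 6.2) describes the endpoint as "Plasma PK (sparse sampling taken pre or 1-2 hours post study drug dosing) in participants randomized to alvelestat", and the endpoint tables in the protocol's Synopsis and section 4.0 carry the same restriction. Neither document defines evaluable.

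On precedence, protocol 10.3 says that the SAP "will describe the selection of participants to be included in the analyses", and the SAP Preface says that it describes and builds on the protocol's statistical content. Neither document ranks one above the other.

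**The concern.** Safety and tolerability are the primary question, and protocol 10.3.1 runs every safety analysis on this set. If delivered and assigned product ever differ, the two documents give different safety tables. Under the protocol rule, an event in a placebo-randomized patient who was actually taking alvelestat adds to the placebo rate and is missing from the alvelestat rate. With 15 patients, one person is a large share of an arm. If the rule is still open when the treatment codes are known, choosing it becomes a post hoc decision on the primary endpoint.

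The PK restriction is a related gap. A placebo-randomized patient who took alvelestat is excluded from the PK Set. The planned comparison of safety findings with exposure (protocol 10.3.1) could then lack that patient's drug level. In the other direction, an alvelestat-randomized patient who was given placebo belongs to the PK Set if the sample is accepted as evaluable.

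**Working it through.** The plan states no figure on this point, so there is none to reproduce. The check compares the texts and then moves one patient between arms.

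**Texts side by side**
- Membership: the same in protocol 10.2 and SAP 7.3.
- Arm assignment: randomized (protocol, stated twice) against actual (SAP).
- Precedence: protocol 10.3 leaves the selection of participants to the SAP. Selection is not in dispute here; the arm in which a participant is counted is. Neither that sentence nor the SAP Preface settles it.

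**Inputs for the illustration**
- Arm sizes: 10 alvelestat and 5 control (protocol 5.2), or 7-8 per arm (SAP 5.4, Table 1). The conflict between the 2:1 and 1:1 ratios is a separate matter; both are used here only to set the range.
- Assumptions: exactly one placebo-randomized patient receives alvelestat instead and has an event; e events occur among the alvelestat-randomized patients; the rest of the placebo arm has none.

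**Formulas**, with a alvelestat and p placebo patients as randomized:
- As randomized: e/a - 1/p
- As treated: (e+1)/(a+1) - 0/(p-1)

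**Results at 10:5**
- e = 0: 0/10 - 1/5 = -20.0 points; 1/11 - 0/4 = +9.1 points
- e = 2: 2/10 - 1/5 = 0.0 points; 3/11 - 0/4 = +27.3 points
- e = 4: 4/10 - 1/5 = +20.0 points; 5/11 - 0/4 = +45.5 points

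The choice of rule moves the difference by 29.1, 27.3 and 25.5 points respectively. The sign reverses only when e/10 is below 1/5, that is, with e = 0 or 1.

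**Result at 8:7 (SAP)**
- e = 2: 2/8 - 1/7 = +10.7 points; 3/9 - 0/6 = +33.3 points

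One patient is 1/5 = 20.0% of the protocol's placebo arm, or 1/8 to 1/7 = 12.5% to 14.3% of an arm under the SAP.

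**PK, opposite error** (one alvelestat-randomized patient given placebo, sample accepted as evaluable and counted as zero)
- The mean concentration falls by 1/10 = 10.0% with 10 patients, and by 12.5% to 14.3% with 8 or 7.
- Protocol 5.5 predicts troughs above 300 nM in about 90% of participants at the target dose. With one such patient, the expected share is 0.90 × 9/10 = 81.0% with 10 patients, 0.90 × 7/8 = 78.8% with 8 and 0.90 × 6/7 = 77.1% with 7.

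**The case against.** The strongest reply is that the SAP already has the as-treated rule, so the harm arises only if the protocol wording prevails. It also needs a dispensing error, and none is reported. Safeguards exist: a computer-generated list used in sequence through the research pharmacy (SAP 5.5), an unblinded pharmacist who labels and accounts for drug (SAP 5.5.2), and recording of doses and departures from the regimen (protocol 7.5, SAP 5.7). With 15 patients, all AEs are listed by participant (protocol 10.3.1) and deaths and SAEs get narratives (SAP 8.3), so a known misallocation could be explained individually. The pilot is not powered, and one-event differences say little: Fisher's exact test gives p = 0.33 for 0/10 versus 1/5 and p = 1.0 for 1/11 versus 0/4. PK is secondary and descriptive.

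Much of this stands, and it limits the point. It does not remove the contradiction, because neither document says that the SAP rule prevails, and listings do not tell the reader which summary table is the planned one.

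Three stronger readings are tempting but not supported:
- A reader might infer that one dispensing error would put both drug toxicity into the placebo arm and placebo plasma into the PK result. These need opposite errors. Alvelestat given to a placebo-randomized patient can cause the first, and also the PK omission. Placebo given to an alvelestat-randomized patient can cause the second. Both arise only from a swap or two separate errors.
- A reader might infer that drug events will be misfiled. That holds only if an error occurs and the protocol rule is applied.
- A reader might infer that the safety comparison generally changes sign. At 10:5 it does so only with at most one other alvelestat event.

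**Conclusion.** The contradiction is certain from the text and concerns the primary population for the primary endpoint. Its effect is conditional: with no wrong product given, the two rules yield identical results. If one placebo-randomized patient did receive alvelestat and had an event, the choice of rule would shift the observed difference by about 25 to 29 points at 10:5 with zero to four other alvelestat events and no other placebo events.

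The PK gap is real but smaller. The restriction to randomized alvelestat patients certainly excludes a placebo-randomized patient who took the drug. Whether placebo plasma could enter turns on the undefined term evaluable. The point should be corrected before database lock because the rule is cheap to settle now and could only be settled post hoc later. It is not evidence that any result is already biased.

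**What to change.** - In protocol 10.2, change both Safety Set sentences to treatment actually received, matching SAP 7.3.
- Define the PK Set as Safety Set participants who actually received alvelestat and have at least one evaluable concentration, and add it to SAP 7.3. Define evaluable, including how a concentration below quantitation in a supposedly dosed patient is handled. Use one term for the matrix, since the PK Set says serum and the endpoint says plasma.
- Align the PK endpoint wording in the protocol Synopsis, protocol 4.0 and SAP 6.2 (Table 3). Otherwise the new PK Set would contradict the endpoint.
- State how a patient who received both products is classified.
- Before database lock, have the unblinded pharmacist or the independent statistician confirm actual treatment by checking accountability records against the randomization list, without unblinding the study team.
- Keep the Full Analysis Set as randomized.

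The cost is a few sentences in each document, with the protocol changes made by amendment and IRB review (protocol Appendix 3), and one check of pharmacy records that are already kept.

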10.3 Statistical Analyses

The main population for safety and tolerability analysis will be the Safety Set. The main population for efficacy analysis will be the Full Analysis Set; supportive analyses will also be performed using the Per-Protocol Set.

Continuous data will be presented using descriptive summaries (e.g., mean, standard deviation, minimum, maximum, median, lower quartile, and upper quartile). Categorical variables will be presented by the number of observations and relative (%) frequency.

Unless otherwise stated, baseline value for any variable will be the last value taken prior to the first dose of study medication.

Unless otherwise stated, all statistical tests will be 2-sided and conducted at the 5% level. All presented confidence intervals will be 2-sided 95% confidence intervals.

Handling of Missing Data

The study is designed to reduce the extent of missing data by alignment of assessments with routine clinical management where possible, by the use of clinical outcomes measures that are expected to be routinely collected for hospitalized patients with COVID-19 and use of telehealth assessments where appropriate to reduce the study burden on patients. However, missing data must be anticipated and handled as follows:

When a patient drops out of a trial full reporting of all reasons for their discontinuation will be collected.

For statistical analyzes missing values are considered a potential source of bias. A multiple imputation of missing data approach will be applied, using pattern mixture model methodology. Within each treatment, 4 proposed data patterns will be defined as follows:

- *Pattern 1: will include patients who completed treatment on study drug*
- *Pattern 2: will include patients who discontinue treatment early due to AEs*
- *Pattern 3: will include patients who discontinue treatment early due to lack of therapeutic efficacy (LOTE)*
- *Pattern 4: will include patients who discontinue treatment early due to reasons other than AE event or LOTE.*

The strategy for dealing with missing values will be further detailed in the statistical analysis plan. If the pattern of missing data is different to that envisaged, including following blinded review of the data at the end of the trial the strategy and the Statistical Analysis Plan (SAP) will be updated.

Descriptive statistical summaries will use Observed Case (OC) data and no missing data values will be imputed.

The SAP will be developed and finalized before database lock and will describe the selection of participants to be included in the analyses and procedures for accounting for missing, unused, and spurious data. Below is a summary of planned statistical analyses of the primary and secondary endpoints.

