5.0 STUDY DESIGN

5.1 Overall Design and Purpose

This is a Phase Ib/II single-center, 2:1 randomized, blinded, placebo-controlled, parallel group, first in disease study. The purpose is to determine the safety, tolerability and PK and explore the mechanistic and clinical effect of alvelestat 240mg orally twice per day for 5 or 10 days added to standard of care in adult patients (≥ 18 years) with COVID-19 respiratory disease.

The study is divided into 3 periods: a screening period, treatment period, and follow up period ([Figure 1](#))

Figure 1: Study Schematic

- **A screening period** from Day -2 to randomization. Eligibility assessments and written informed consent will occur prior to randomization and treatment arm allocation. Serious Adverse Events will be collected during screening.
- **A treatment period** consisting of alvelestat/matched placebo 240 mg/matched placebo bid Days 1 to 5 given on top of standard of care (SoC – per local clinical guidelines). Safety assessments including vital signs, liver and renal function, EKG, and hematology will be assessed at baseline, then as per the Schedule of Assessments (SoA) for the remainder of the 5-day treatment period. Adverse events, vital signs, respiratory support and concomitant medications that may be part of routine clinical care will be collected daily during hospitalization. Blood will be collected at baseline and during study drug treatment to Day 5 for secondary efficacy biomarkers, along with assessment of oxygen deficit assessments (SaO₂/FiO₂). PK sampling will be collected on 2 occasions, at initiation of dosing and at end of treatment (EoT) for steady state analysis. For patients that remain hospitalized at Day 5 due to COVID-19, an optional extension period of treatment to Day 10 may be given and can be referred to on the separate SOA covering this extension. Clinical outcomes of disease progression (respiratory support requirements), disease severity (WHO ordinal scale), will be completed at Baseline (Day 1), during the treatment period to (Day 5 or 10), or EoT and to Day 60 (Clinical Outcome Assessments). Those subjects who are unable to complete the treatment period for any reason, including those discharged from hospital prior to completion of Day 5 or 10, will discontinue study drug and undergo an EoT assessment. Wherever possible they will continue to be followed up in the study.

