5.2 Number of Participants

Approximately 20 subjects will be screened in order to recruit 15 (10 randomized to alvelestat + SoC; 5 randomized to SoC). Subjects who discontinue study drug or the study will not be replaced.

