10.3.2 Efficacy Analyses (Secondary Endpoints)

Comparison of alvelestat and placebo will be performed using an analysis of covariance (ANCOVA) model for continuous variables, with Least Squared means for the difference between pairwise treatment regimens, standard errors, two-sided 95% CIs and P-value for the difference between pairwise treatment regimens.

Categorical variable will be compared between treatments by Chi-square test (or Fisher's exact test as appropriate).

Endpoint	Statistical Analysis Methods
Biomarkers	
Within individual absolute and % change from baseline will be calculated. An analysis of covariance (ANCOVA) model with baseline levels as a covariate and treatment strata as factors will be used to generate least squared means and least squared mean differences between treatment groups. Continuous measures will be log transformed where appropriate.
 
The parameters during treatment will be compared to the baseline values for active and placebo patients separately to evaluate natural variability of the markers.
 
The time-matched biomarker values will be compared between placebo and active groups to assess the differences outside natural variability and time to significant change for the responsive biomarkers.

SaO ₂ /FiO ₂	Within individual absolute and % change from baseline will be calculated.
Disease progression (alive and respiratory failure free)	The proportion alive and respiratory failure free will be presented by the number of observations, absolute and relative (%) frequency.

Endpoint	Statistical Analysis Methods
Other clinical outcomes	
Continuous variables (e.g. duration of hospital/ICU stay) mean, standard deviation, minimum, maximum, median, lower quartile, and upper quartile).
 
Change in level of respiratory support will be presented as shift tables.
 
Time to event (e.g. time to room air, to death, to discharge), will be analysed using Kaplan-Meier methods, and quartiles for the median time to event will be presented together with their 95% confidence intervals. Comparisons between treatment regimens will be performed by means of the log-rank test.

Disease severity (WHO 9-point ordinal scale)	
Change from baseline will be presented as mean, standard deviation, minimum, maximum, median, lower quartile, and upper quartile).
 
Responder analyses (improvement and deterioration) will be presented as number of observations, absolute and relative (%) frequency.

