5.4 Treatments Administered

Once eligibility is confirmed, patients will be randomized in a 1:1 ratio to one of two treatment arms listed in Table 1. Dosing will be performed twice daily approximately 12 hours apart in the morning and evening at approximately the same time each day.

Table 1. COSTA treatment arms.

Treatment Arm	n	Treatment
Treatment Arm 1	7-8	Blinded alvelestat (240 mg) tablets BID + SoC*
Treatment Arm 2	7-8	Blinded placebo tablets BID + SoC*

Abbreviations: SoC= standard of care, BID= twice daily, *SoC treatment for COVID-19 infection based on established practices within UAB

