7.4 Missing Data

All attempts will be made to collect all data per protocol.

- The patients withdrawn from treatment will be followed up regarding their status according to the WHO Ordinal Scale at Day 29 as far as possible (exceptions for patients with withdrawn consent or lost to follow-up) and this data will be the primary source for handling missing data in the study.

Any data point that appears to be erroneous or inexplicable based on clinical judgment will be investigated as a possible outlier.

- If data points are identified as outliers, sensitivity analyses may be performed to examine the impact of including or excluding the outliers. Any substantive differences in these analyses will be reported.

For survival analyses, patients with death as outcome will be censored at Day 29 (Day 60), unless the required event was reached prior to death. Patients who are lost to follow-up or terminate the study prior to Day 29 (Day 60) for other reason than death and prior to observing/experiencing the event will be censored at the time of their last observed assessment. The only time to event analyses is the time to recovery.

For secondary endpoint analyses, the following imputation rules will be used for patients who are lost to follow-up, terminate early from the study, or do not have further outcome data available after discharge for any reason than death:

- Patients with no data collected at the actual time point of interest for other reason than death, the last assessment of their status prior to this time point will be used as a representative for that time point. Especially, if the patient's clinical status scale is 1 or 2 at the last observed assessment, then the patient will be considered to be recovered through Day 29.
- For endpoints assessing total time (oxygen or non-invasive ventilator care), the status for patients with no data collected for other reason than death, will be assumed unchanged from last assessment of the score up to last day in the definition of the endpoint (Day 29). Thus, no extra days will be added for patients without oxygen or patients without non-invasive ventilator care at last assessment.
- Patients that die in the study will be handled as worst case in all the analyses, that is they are considered to be on oxygen need, non-invasive and invasive mechanical ventilator need for all time points following the death.

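### The protocol's four-pattern imputation is not estimable as separate models in 15 patients, and the SAP replaces it without comment by carrying the last status forward, which presumes a good outcome for patients lost after discharge

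*Protocol*

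**What the plan says.** **Protocol.** Section 10.3 commits to a method: "A multiple imputation of missing data approach will be applied, using pattern mixture model methodology". Within each treatment it proposes four patterns: completed treatment, stopped for an adverse event, stopped for lack of efficacy, and stopped for any other reason. It gives no imputation model, identifying restriction or number of imputations, and leaves further detail to the SAP. Descriptive summaries are to use observed cases without imputation. On early discharge, section 5.1 says that patients unable to complete treatment, "including those discharged from hospital prior to completion of Day 5 or 10, will discontinue study drug and undergo an EoT assessment". For outcomes such as death, section 10.3.2 says: "Time to event (e.g. time to room air, to death, to discharge), will be analysed using Kaplan-Meier methods". Section 10.3.1 also plans the count and percentage dead by Day 90.

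**SAP.** Section 7.4 mentions neither multiple imputation nor patterns. For secondary endpoints in patients without data at a time point for a reason other than death, "the last assessment of their status prior to this time point will be used as a representative for that time point". A last score of 1 or 2 counts as recovered through Day 29, and a discharged patient without further hospital data is taken as not readmitted. Table 2 ties discharge itself to a score of 1 or 2. Known deaths are scored as worst case. In survival analyses, patients lost before the event are censored, and 7.4 names time to recovery as the only such analysis. All-cause mortality is one of the proportions in 8.4.2, tabulated in Table 11 at Days 29, 60 and 90.

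**The concern.** The two documents prescribe different treatments of the same missing values. The SAP presents itself as expanding on the protocol's statistics, yet it neither says that the method has changed nor gives a reason. Protocol 10.3 allows the strategy to be updated if missingness differs from what was expected, but the SAP does not invoke that clause.

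Neither rule is satisfactory as it stands. The protocol's rule asks for more patterns than the arms can fill. Its patterns also fit the likely gaps poorly. They are defined by why treatment stopped, whereas most missing data at Days 29 to 90 would come from loss after discharge. Someone lost after finishing treatment sits with the completers. Someone discharged early because of improvement sits, under Protocol 5.1, with withdrawals for other reasons.

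The SAP's rule resolves the commonest kind of loss in the favourable direction and then analyses the result as if it had been seen. In arms this small, one such patient changes the reading of recovery, re-hospitalization or mortality, which Protocol 10.1 wants examined for signals to support further development.

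**Working it through.** **Inputs.**
- Size and split: Protocol 10.1, "15 participants will be randomized in a 2:1 ratio"; Protocol 5.2, "10 randomized to alvelestat + SoC; 5 randomized to SoC"; SAP 5.4, "patients will be randomized in a 1:1 ratio to one of two treatment arms listed in Table 1", with 7-8 per arm in its Table 1. The allocations conflict, so both are carried through.
- Basis for the size: Protocol 10.1 says that "it is not formally powered based on any specific endpoint". There is no power or precision figure to reproduce. The split does reproduce: 15 × 2/3 = 10 and 15 × 1/3 = 5.
- Patterns: 4 within each arm (Protocol 10.3).
- Discontinuation and loss rates: not given, so a range is assumed below.
- Recovery: the SAP does not define it. I take it as a score of 1 or 2, as 7.4 uses it.

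**1. Cells.** 4 patterns × 2 arms = 8 cells, and 15/8 = 1.9 patients per cell. By arm size: 5/4 = 1.25, 7/4 = 1.75, 8/4 = 2.0, 10/4 = 2.5.

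**2. Minimum for separate models.** A within-pattern regression with intercept, baseline slope and residual variance has 3 parameters, so it needs at least 3 observed patients per pattern. That is 4 × 3 = 12 per arm, or 24 in all. The largest arm under either document is 10.

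**3. Chance that the cells are even occupied.** Let a fraction d stop treatment, split equally over the three stopping patterns (assumption). Each arm is then multinomial with probabilities (1−d, d/3, d/3, d/3), and the chance that all four patterns hold at least one patient is multiplied over the two arms. At d = 30% and 10/5 this is 0.2478 × 0.0420 = 0.0104.

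| d | 10/5 | 7/8 |
|---|---|---|
| 20% | 0.1% | 0.2% |
| 30% | 1.0% | 1.7% |
| 40% | 3.5% | 5.9% |
| 75% | 18% | 32% |

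At 75% the four patterns are equally likely, which is the case most favourable to filling them.

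**4. A restricted version.** If every imputation borrowed from the completers of the same arm, residual degrees of freedom would be n − discontinued − 2. For a placebo arm of 5 this gives 3, 2 and 1 with none, one and two discontinued.

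**5. Carry-forward after discharge.** One patient is worth 1/10 = 10 points or 1/5 = 20 points at 10/5, and 1/8 = 12.5 or 1/7 = 14.3 points at 7-8 per arm. Carry-forward scores each lost discharged patient as recovered. With L lost per arm, the risk difference (alvelestat minus placebo) can therefore lie anywhere from L_A/n_A below to L_P/n_P above the carry-forward value. With one lost in each arm:
- 10/5: from −10 to +20 points, a span of 30.
- 7/8: from −14.3 to +12.5 points, a span of 26.8.
- 8/7: from −12.5 to +14.3 points, again 26.8.

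**6. Missed deaths, as illustration only.** Protocol 5.8 cites inpatient case fatality of 14.9% (women) and 23.5% (men). If lost patients died at those rates, the chance of at least one unseen death among k lost is 1 − (1−p)^k. That is 15% to 24% for k = 1. For k = 2 it is 1 − 0.851² = 28% to 1 − 0.765² = 41%. Patients well enough to be discharged may be at lower risk, so these figures may be too high.

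**The case against.** Much can be said for the plan.

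*The imputation might run in some form.* The patterns are only proposed, empty ones need no imputation, and a model borrowing from completers or from placebo could be fitted. A reader might infer that pattern-mixture imputation is impossible here, and the documents do not support that. What stands is narrower: separate models per pattern are not estimable, no restriction is specified, and one that borrows only from same-arm completers would rest on very few degrees of freedom.

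*Carry-forward does not reach every secondary endpoint.* SAP 7.4 and 8.4.1 censor time to recovery. The rule concerns status, so it does not clearly cover the biomarker ANCOVA, for which missing values are simply not addressed.

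*The direction is not one-sided.* A patient last seen on oxygen stays on oxygen to Day 29, and known deaths are worst case. A general upward bias in recovery is not shown; only the subgroup lost after discharge is resolved favourably.

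*The SAP never says that lost patients are alive.* Its text says recovered, and only through Day 29. Alive at Days 29, 60 and 90 follows from applying the general rule to the mortality proportion. It is an inference, though no other rule for unknown vital status is given.

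*A mortality proportion is not itself a departure,* since Protocol 10.3.1 plans one. The departure is the absence of a time-to-death analysis. The composite safety event in SAP 7.6 and 8.3 includes death but does not replace it.

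*Early discharge may not be discontinuation.* SAP 5.5.1 doses until discharge or Day 10, and its compliance table sets discharge aside. That conflicts with Protocol 5.1 and leaves the pattern for these patients unsettled.

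*Safeguards exist.* SAP 7.4 makes Day 29 follow-up of withdrawn patients its primary source for handling missing data, and Protocol 7.3 and SAP 5.5.2 keep the data blinded while rules can still change. This reduces the problem but does not remove it for patients who cannot be reached.

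**Conclusion.** The concern holds in limited form. The protocol and SAP give conflicting missing-data rules. The protocol's rule, read as separate models in 8 cells, cannot be estimated at 10/5 or at 7-8 per arm. The SAP's single carry-forward presumes recovery and no readmission after discharge and, by inference, survival. Because imputed statuses are analysed as observed, intervals for those endpoints are too narrow.

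Each lost patient can move an arm's proportion by 10 or 20 points at 10/5, or by 12.5 to 14.3 at 7-8 per arm. The 30-point and 27-point spans assume exactly one patient lost after discharge in each arm; no loss rate is stated, and with no loss the effect is nil. The documents do not support a claim that recovery is overstated, or mortality understated, across all lost patients.

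Importance is moderate. Protocol 10.1 calls the efficacy analyses exploratory and SAP 7.2 calls all analyses so. The primary safety tables do not depend on this rule.

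**What to change.** Reconcile the two documents before unblinding:

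1. Delete the four-pattern imputation from Protocol 10.3 and refer to SAP 7.4.
2. In SAP 7.4, state that the biomarker ANCOVA uses observed cases.
3. Add to the SAP a Kaplan-Meier analysis of time to death, as Protocol 10.3.2 already plans, censoring at the last date known alive. Present it beside the Day 90 count and percentage, and report by arm how many have unknown vital status.
4. For the binary respiratory, WHO-scale, recovery and re-hospitalization endpoints, show carry-forward only beside best-case and worst-case bounds, with the number of imputed patients per arm.

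The cost is wording and extra table columns. The bounds may be wide, as the spans above show, and that has to be accepted. The Kaplan-Meier estimate assumes non-informative censoring and may overstate mortality if patients lost after discharge are at lower risk than those still followed; say so beside the result.
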